Sponsor: PROMOMED RUS LLC, Russia	Separate study table relating to part of the dossier	(For use by national authorized bodies only)
Name of finished product: Areplivir, film-coated tablets	Volume: Pages:	
Active ingredient: Favipiravir		
Investigational medicinal product, dose and mode of administration, batch number: Investigational medicinal product: Areplivir, film coated tablets (PROMOMED RUS LLC, Russia), batch 010520 (expiry date 06.2022). Patients in Arm 1 take the investigational product Areplivir, film coated tablets: on Day 1st of treatment - 1600 mg (8 tablets) 2 times a day; on days 2-14 of treatment - 600 mg (3 tablets) 2 times a day. The drug is taken orally every 12 hours, swallowing whole tablet without chewing and washing down with a glass of water. The course of treatment is 14 days. The test drug is administered in hospital setting under supervision of a clinical investigator. The test drug is not handed over to the patient.		
Duration of the study: The total duration of the study for the patient is not more than 31 days, of which the screening period is not more than 2 days. Visits: Visit 0 (screening, not more than 2 days); Visit 1 (randomization, day 1)*; Visit 2 (day 5); Visit 3 (day 10); Visit 4 (day 15)**; Visit 5 (day 21±1)***; Visit 6 (study completion, day 28±1)***. * Visit 1 may coincide with Visit 0. ** If a patient is discharged from hospital at an earlier date, the visit will be conducted at the time of discharge (for Arm 2 patients). *** If a patient is discharged from hospital at an earlier date, then this patient does not need to visit the study site. Fatalities and serious adverse events (SAE) will be followed-up through telephone contact with the patient. Discharge of patients from a hospital is carried out in accordance with the local practice of the study site in compliance with the current sanitary and epidemiological regime.		
Efficacy criteria: The efficacy of therapy is assessed using the following endpoints: Primary efficacy criterion: 
 • Time (in days) to improvement in clinical status by categorical ordinal scale of clinical status improvement. • Rate of clinical status improvement by categorical ordinal scale of clinical status improvement by 2 or more categories at Visit 3. Secondary efficacy criteria:		

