Sponsor: PROMOMED RUS LLC, Russia	Separate study table relating to part of the dossier Volume: Pages:	(For use by national authorized bodies only)																			
Name of finished product: Areplivir, film-coated tablets																					
Active ingredient: Favipiravir																					

 Percentage of patients with elimination* of COVID-19 according to PCR data at Visit 3. Time (in days) to end of fever (body temperature < 37.2 ° C for 3 consecutive days without antipyretic medication). Assessment of lung injury according to CT data at Visits 4, 5 and 6. Percentage of patients transferred to intensive care unit. Percentage of cases with non-invasive lung ventilation. Percentage of cases with mechanical lung ventilation. Incidence of fatal cases. 
* Elimination of the virus is defined as two negative laboratory results for the presence of SARS-CoV-2 RNA obtained at an interval of 24 hours.
 
Safety criteria:
 
 Total number of adverse events (AEs) stratified by severity and incidence; Incidence of adverse drug reactions; Incidence of serious adverse events (SAEs) associated with the use of the study drug/standard therapy; Percentage of patients with at least one AE; Percentage of patients who discontinuation treatment due to AE. 																					

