- Percentage of cases with non-invasive lung ventilation.
- Percentage of cases with mechanical lung ventilation.
- Incidence of fatal cases.
- Assessment of lung injury according to CT data at Visits 4, 5 and 6.**

* Virus elimination is defined as two negative laboratory tests for SARS-CoV-2 RNA obtained at intervals of 24 hours.

**An "empirical" visual scale will be used to estimate changes in lung involvement from CT data.

For the analysis of these parameters, an intergroup comparison of shares is used using a two-sided version of the **Fischer's exact test** (or a two-sided version of the χ^2 (chi-square) test, if all the expected values in the cells of the contingency table for this analysis are 5 or more).

The protocol also includes the following endpoint:

- Time (in days) to fever disappearance (body temperature < 37.2 ° C for 3 consecutive days

Sponsor: PROMOMED RUS LLC, Russia	Separate study table relating to part of the dossier	(For use by national authorized bodies only)
Name of finished product: Areplivir, film-coated tablets	Volume: Pages:	
Active ingredient: Favipiravir		

without antipyretic medication).

For the secondary efficacy parameter "time (in days) to fever disappearance (body temperature < 37.2 °C for 3 consecutive days without antipyretic drugs), a comparison between arms is made using the *Student's t-test* or the *Mann-Whitney test* (depending on the nature of the distribution of quantitative indicators). Also, *Kaplan-Meier technique* and the construction of *survival tables* can be used as descriptive methods of study. The *Gehan-Wilcoxon test, the Cox-Mentel test or the Log-Rank test* can be used to compare the time (in days) to the disappearance of fever in the study arms.

Analysis of secondary efficacy parameters is performed in the ITT population (main analysis), and in the PP population (additional analysis).

In case of developing acute respiratory distress syndrome and the need to switch patient to mechanical ventilation, the investigational drug is canceled, but the patient is not withdrawn from the study. Patients are under follow-up until Visit 6, the data are taken into account to assess efficacy in the ITT population.

Safety Analysis

Safety criteria

Safety assessment includes the following parameters:

- Total number of adverse events (AEs) stratified by severity and incidence;
- Incidence of adverse drug reactions;

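### Time to end of fever is compared by t-test or Mann-Whitney with no rule for unresolved fever, although observation can end earlier in Arm 2; this can bias the comparison and lose power

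*Combined protocol and SAP*

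**What the plan says.** Among the secondary efficacy criteria the Synopsis lists "Time (in days) to end of fever", defined as a temperature below 37.2 °C "C for 3 consecutive days" without antipyretics. The endpoint therefore needs three observed days to be established.

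Under Analysis of secondary efficacy parameters, the named method is the t-test or Mann-Whitney test, chosen by the shape of the distribution: "without antipyretic drugs), a comparison between arms is made using the" one or the other. Kaplan-Meier curves and survival tables are allowed as description. The Gehan-Wilcoxon, Cox-Mantel (printed Cox-Mentel) or log-rank test "can be used to compare the time (in days) to the disappearance of fever in the study arms". Nothing says when, or which result counts if they disagree.

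On follow-up, Duration of the study says that if a patient leaves hospital before Visit 4 (day 15), "the visit will be conducted at the time of discharge (for Arm 2 patients" only). For Visits 5 and 6, "If a patient is discharged from hospital at an earlier date, then this patient does not need to visit the study site"; the telephone contact that replaces them covers deaths and serious adverse events. For Arm 1, "The course of treatment is 14 days" and "The test drug is not handed over to the patient". Discharge otherwise follows local practice.

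The missing-data section applies last observation carried forward to the main endpoint. It gives no rule for this one.

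**The concern.** A t-test or Mann-Whitney test needs a number of days for every patient. A patient who dies, never becomes afebrile, or is discharged before three afebrile days are recorded has none. The analyst must then drop that patient or enter the last observed day, and the plan does not say which. Either choice shortens recorded times most in the arm observed for less time. If that is Arm 2, standard therapy looks faster than it is.

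Two things are at stake. Equal treatments can appear different, and a real benefit of Areplivir can be hidden. The unranked list of tests also leaves room, in an open-label trial, to choose the test after seeing the data. The endpoint is secondary, but Justification of sample size lets stage 1 select a criterion from the secondary ones, so it could gain weight. The primary time endpoint has similar wording in its own section, and amending that would leave this text unchanged.

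**Working it through.** **Figures in the plan.** None concerns this endpoint. The printed powers (0.4553 at 40 per arm, 0.80170 at 107 per arm) are for the responder proportion.

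**Inputs from the plan.** 100 per arm; two-sided 0.05; Visit 4 at day 15, or at discharge for Arm 2.

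**Assumptions, not in the plan.** Fever resolves at 0.12 per day in both arms. Arm 1 is observed to day 15. A share q of Arm 2 leaves on days 5-14, evenly spread and unrelated to fever; the rest is observed to day 15.

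**Step 1: unresolved at end of observation.** The share still unresolved at day c is S(c) = exp(-0.12c).
- Day 15: exp(-1.8) = 0.165.
- Average of S(c) over days 5-14: 0.339.
- Arm 2 at q = 50%: 0.5 × 0.165 + 0.5 × 0.339 = 0.252, against 0.165 in Arm 1.

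**Step 2: apparent difference when the arms are equal.** Let p = 1 - exp(-0.12) = 0.113.
- *Last day entered.* The mean recorded time for observation to day c is (1 - S(c))/p. This is 7.38 days at day 15 and 5.84 on average over days 5-14. Arm 1 appears slower by q × (7.38 - 5.84) = q × 1.54, that is 0.46, 0.77 and 1.08 days at q = 30, 50 and 70%.
- *Unresolved dropped.* The sum of resolved times per patient is (1 - S(c))/p - c·S(c), which is 4.90 at day 15 and 2.95 on average over days 5-14. The Arm 1 mean is 4.90/(1 - 0.165) = 5.87. At q = 50% the Arm 2 mean is (0.5 × 4.90 + 0.5 × 2.95)/(1 - 0.252) = 5.25, a difference of 0.62 days. At 30% and 70% it is 0.36 and 0.91.

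**Step 3: simulated rejection rates, equal arms, same inputs.**

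| Share of Arm 2 leaving early | t-test, observed times | Mann-Whitney, observed times | Log-rank |
|---|---|---|---|
| 30% | about 9% | about 9% | about 5% |
| 50% | about 16% | about 14% | about 5% |
| 70% | about 32% | about 24% | about 5% |

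With the last day entered, the t-test rejects in about 11/20/38%.

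**Step 4: power at a true hazard ratio of 1.5, 50% leaving early.** The t-test has about 7% (unresolved dropped) or 32% (last day entered); log-rank has about 72%.

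**Step 5: a different fever distribution.** Gamma times (shape 2.5, mean 5 or 7 days), three observed afebrile days required, 25-75% of Arm 2 leaving on days 7-14, 1,000 runs per setting:
- No early discharge: all tests reject 4.5% to 5.1%.
- Unresolved dropped: Arm 1 appears 0.17 to 0.84 days slower; t-test 6.5% to 45.0%, Mann-Whitney 5.7% to 39.7%.
- Last day entered: 0.06 to 0.51 days slower; t-test 5.0% to 17.1%, Mann-Whitney 4.3% to 8.7%.
- Log-rank: 3.9% to 5.3%.

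**Step 6: discharge tied to fever.** The same gamma model, with 50% of Arm 2 leaving 0-5 days after fever ends. The t-test and Mann-Whitney shift is -0.10 to +0.04 days, and they reject 3.8% to 5.6%. Log-rank now rejects 15.1% to 15.6%; a separate run gave 16-20%. The reason is that two of the six possible delays (0 and 1 day) cut off the three-day run, so about 50% × 2/6 = 17% of Arm 2 is censored just before its event. At a mean of 5 days, unresolved shares are 2.3% in Arm 1 and 18.0% in Arm 2. This makes Arm 2 look slower, the opposite direction from Steps 2-5.

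**The case against.** The strongest objection is that patients usually go home once fever has settled. In that case the t-test and Mann-Whitney bias is near zero (Step 6), while log-rank with censoring at discharge becomes the distorted test. This stands: changing the test alone could make matters worse.

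A reader might infer that the planned comparison is biased as a matter of fact. The documents do not support that. They give neither the share of Arm 2 leaving before three afebrile days nor the coding of such patients, and they also allow time-to-event tests. Arm 1's stay to about day 15 is itself an inference from in-hospital dosing and from a footnote restricted to Arm 2; no sentence forbids earlier discharge.

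A reader might also infer that the flaw could manufacture a superiority claim for Areplivir. In the scenarios where the t-test and Mann-Whitney are materially biased, the error runs against Areplivir. Larger error rates arise if Arm 1 is assumed to be observed to day 28, but the visit footnote releases any discharged patient from Visits 5 and 6, so day 15 fits the text better.

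Promotion of fever to a confirmatory endpoint is possible but speculative, and the plan then promises a multiplicity adjustment and a recalculated sample size. The text reviewed is a synopsis that refers to a final statistical analysis plan, so a censoring rule may exist elsewhere.

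**Conclusion.** The point holds as a gap in the analysis rule. The stated default ignores censoring, the suitable methods are optional and unranked, and an unresolved patient has no defined value, for an endpoint whose observation can end earlier in Arm 2.

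The consequence is conditional. If early discharge is unrelated to fever, equal arms can appear to differ by 0.06 to 1.08 days across the settings tried, to Areplivir's disadvantage. False rejection then ranges from about nominal to 45%, and t-test power can fall from about 72% (log-rank) to between 7% and 32%. If discharge follows resolution, the default tests show almost no bias. All sizes rest on assumed fever times and discharge patterns, with Arm 1 observed to day 15. The endpoint is secondary, so the main superiority claim does not rest on it. The plan should be changed; confidence is medium.

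**What to change.** 1. Name Kaplan-Meier with a two-sided log-rank test as the analysis, with a Cox hazard ratio as the estimate, and remove the t-test/Mann-Whitney default for this endpoint.
2. Define the event date (first or third day of the afebrile run) and censor unresolved patients at the last temperature record. Keep patients who die before resolution in the risk set as unresolved to the common end day.
3. Record temperature and antipyretic use to the same day in both arms, for example by adding these questions to the existing telephone contact. Where that is not possible, report a sensitivity analysis that counts discharge while afebrile as resolution. Without one of these, log-rank is open to the distortion in Step 6.

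Items 1 and 2 are wording changes, since log-rank and Kaplan-Meier are already listed. Item 3 costs slightly more data collection, or one additional analysis.

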2. OVERVIEW (SYNOPSIS)

Sponsor: PROMOMED RUS LLC, Russia	Separate study table relating to part of the dossier	(For use by national authorized bodies only)
Name of finished product: Areplivir, film-coated tablets	Volume: Pages:	
Active ingredient: Favipiravir		
Protocol No.: FAV052020		
Clinical study name: Open randomized multicenter comparative study on the efficacy and safety of Areplivir film-coated tablets (PROMOMED RUS LLC, Russia) in patients hospitalized with COVID-19		
Investigators, Study site: The study is conducted at five research centers in the Russian Federation. Detailed information is provided in Section 6.		
Publication: A list of scientific papers and publications relevant to this study will be presented in the Clinical Study Final Report.		
Study period: Q2 2020 – Q4 2020	Drug development phase: III	
Study purpose: Assess the efficacy and safety of Areplivir versus standard therapy in patients hospitalized with COVID-19. Study objectives: 
 • Assess the efficacy of Areplivir versus standard therapy in patients hospitalized with COVID-19. • Assess the safety of Areplivir versus standard therapy in patients hospitalized with COVID-19. 		
Methodology: an open randomized multicenter comparative study on the efficacy and safety of Areplivir in patients hospitalized with COVID-19.		
Number of patients (planned and included in the analysis): The study will randomize 200 patients. Given the possible non-inclusion of patients at the screening stage, the maximum number of patients to sign the Informed Consent Form in the Patient Information Leaflet and to participate in screening can be no more than 210 people. This interim report is based on data on 80 patients (40 patients in the Areplivir arm + 40 patients in the standard therapy arm). Patients who met the inclusion criteria and did not meet the non-inclusion criteria were randomized to 2 groups (treatment arms) in a 1:1 ratio: Arm 1 (n=100) receives the study drug Areplivir film-coated tablets: on day 1 of therapy - 1600 mg (8 tablets) 2 times a day; on days 2-14 of treatment - 600 mg (3 tablets) 2 times a day. The drug is taken orally every 12 hours, swallowing whole tablet without chewing and washing down with a glass of water. The course of treatment is 14 days.		

Sponsor: PROMOMED RUS LLC, Russia	Separate study table relating to part of the dossier	(For use by national authorized bodies only)

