
Sponsor: PROMOMED RUS LLC, Russia	Separate study table relating to part of the dossier	(For use by national authorized bodies only)
Name of finished product: Areplivir, film-coated tablets	Volume: Pages:	
Active ingredient: Favipiravir		

The proof of the superiority hypothesis is the establishment of a statistically significant time difference (in days) before patient's clinical status improvement between the Areplivir arm and the standard therapy arm.

The next primary efficacy parameter is the percentage of patients who achieved an improvement in clinical status according to the categorical ordinal scale of clinical improvement by 2 or more categories at Visit 3.

- Rate of clinical status improvement by categorical ordinal scale of clinical status improvement by 2 or more categories at Visit 3.

For the analysis of this parameter, an intergroup comparison of percentages is used using a two-sided version of the **Fischer's exact test** (or a two-sided version of the χ^2 (chi-square) test, if all the expected values in the cells of the contingency table for this analysis are 5 or more). The percentage of patients who achieved improvement in clinical status on a categorical ordinal clinical improvement scale by 2 or more categories at Visit 3 is presented with a two-sided 95% confidence interval by treatment arm. Hypothesis testing is performed at a 5% significance level. The difference in proportion between treatment arms and the 95% bilateral confidence interval for the difference in proportion calculated by **Newcomb-Wilson technique is presented**.

The proof of the hypothesis of superiority of Areplivir film-coated tablets (PROMOMED RUS LLC, Russia) is the establishment of a statistically significant difference in the proportions of patients who achieved an improvement in clinical status according to the categorical ordinal scale of clinical improvement by 2 or more categories at Visit 3, between Areplivir arm and standard therapy arm.

Analysis of the primary efficacy parameter is performed in the ITT population (main analysis), and in the PP population (additional analysis). A summary of all efficacy indicators is provided.

Analysis of secondary efficacy parameters

The following efficacy parameters in the protocol are represented by qualitative values:

- Percentage of patients with elimination * COVID-19 according to PCR analysis at Visit 3.
- Percentage of patients transferred to intensive care unit.

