- Incidence of serious adverse events (SAEs) associated with the use of the study drug/standard therapy;
- Percentage of patients with at least one AE;
- Percentage of patients who discontinuation treatment due to AE.

Cross-group comparisons are performed for all safety indicators. The comparison of groups on frequency indicators is carried out using the *Fischer's exact test* or the χ^2 (chi-square) test, depending on the expected value in the cells of contingency table. For quantitative laboratory results, comparisons between groups at relevant visits are made using the *Student's t-test* or the *Mann-Whitney test* (depending on the nature of the distribution of quantitative indicators).

For analysis of all safety parameters the safety population was used.

In case of developing acute respiratory distress syndrome and the need to switch patient to mechanical ventilation, the investigational drug is canceled, but the patient is not withdrawn from the study. Patients are under follow-up until Visit 6, the data are taken into account to assess efficacy in the ITT population.

Interim analysis

In the first stage, 40 patients were included in each group (study arm). Given 40 patients in each of the study arms, the sensitivity of the study to confirm 15% superiority by incidence, supposing the expected response 80% in the test drug arm, will exceed 45%.

Sponsor: PROMOMED RUS LLC, Russia	Separate study table relating to part of the dossier	(For use by national authorized bodies only)
Name of finished product: Areplivir, film-coated tablets	Volume: Pages:	
Active ingredient: Favipiravir		

Two Independent Proportions (Null Case) Power Analysis									
Numeric Results of Tests Based on the Difference: P1 - P2									
H0: P1 - P2 ≥ 0. H1: P1 - P2 = D1 < 0. Test Statistic: Z test with pooled variance									
		Sample Size	Sample Size	Prop H1	Prop				
		Grp 1	Grp 2	Grp 1 or	Grp 2 or	Diff	Diff	Target	Actu
	Power	N1	N2	Trtmnt	Control	if H0	if H1	Alpha	Alpha
				P1	P2	D0	D1		
	0.4553	40	40	0.6500	0.8000	0.0000	-0.1500	0.0500	0.0500

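### The only listed SAE indicator is treatment-related SAEs, so the between-arm SAE comparison in this open trial depends on a causality judgement

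*Combined protocol and SAP*

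**What the plan says.** The plan is set out in section 2, Overview (Synopsis). Its Safety criteria list has one line on serious events: "Incidence of serious adverse events (SAEs) associated with the use of the study drug/standard therapy". The list under Safety Analysis repeats that line word for word. The Safety Analysis text adds: "Cross-group comparisons are performed for all safety indicators". Frequencies are to be tested with Fisher's exact test or chi-square in the safety population.

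The adverse event lines beside it carry no such qualifier: "Total number of adverse events (AEs) stratified by severity and incidence" and "Percentage of patients with at least one AE". The remaining safety lines are adverse drug reactions and discontinuation because of an adverse event.

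The secondary efficacy criteria include "Incidence of fatal cases", "Percentage of patients transferred to intensive care unit", "Percentage of cases with mechanical lung ventilation" and non-invasive ventilation, none limited by cause. They are analysed in the ITT set, with PP as an additional analysis.

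The Methodology entry calls the trial "an open randomized multicenter comparative study on the efficacy and safety of Areplivir in patients hospitalized with COVID-19". No blinded causality assessor or adjudication committee is described. The only independence safeguard, under General methods of analysis, concerns statistical data processing. Under Duration of the study, deaths and SAEs after early discharge are followed by telephone, with no filter on relatedness.

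**The concern.** Randomisation makes the arms comparable for the number of patients who have an SAE. It does not do so for the number whose SAE someone decides to attribute to treatment, because that decision comes after randomisation and, in an open trial, can depend on the arm. The question asked also differs between arms: in Arm 1 it concerns chiefly one named tablet, in Arm 2 a regimen that the investigator chooses by guideline and drug availability. Even a careful assessor would find it hard to apply one threshold to both.

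Two things are at stake. If attribution differs between arms, the test can show a difference in serious events that does not exist, in either direction. If attribution is equal, the counts shrink and a real excess becomes harder to see. Safety is one of the two stated objectives, and this is the only SAE comparison listed.

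**Working it through.** **No stated figure to reproduce.** The plan gives no SAE rate, no attribution rate and no power for safety. Its power figures concern the responder endpoint.

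**What each listed comparison captures**

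| Comparison | Filtered by causality? | Limited to serious events? |
|---|---|---|
| Related SAEs | Yes | Yes |
| Adverse drug reactions | Yes | No |
| AEs by severity | No | No (severity is not seriousness) |
| Patients with any AE | No | No |
| Discontinuation for AE | No causality wording | No |
| Death, intensive care, ventilation (efficacy criteria) | No | Only those outcomes |

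No line is both unfiltered and covers all serious events. A hepatic, renal or allergic SAE that leads to no death, intensive care transfer or ventilation is counted as serious only if it is judged related.

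**Illustration.** Inputs from the plan: 100 patients per arm, two-sided level 0.05, Fisher's exact test. Assumed inputs: the all-cause risk of at least one SAE, *p*, and the fraction of patients with an SAE whose event is called related, *a*.

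The probability that a patient counts in the listed indicator is *r = p × a*, separately by arm. With *X*₁ ~ Bin(100, *r*₁) and *X*₂ ~ Bin(100, *r*₂), the chance of a significant result is the sum of P(*X*₁ = *i*) × P(*X*₂ = *j*) over all tables (*i*, *j*) with Fisher p ≤ 0.05. The sums were enumerated exactly.

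*Equal true risk in both arms: any significant result is false*

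| All-cause risk, both arms | Attributed, Arm 1 vs Arm 2 | Related SAE risk | Related-SAE test | All-cause test |
|---|---|---|---|---|
| 10% | 50% vs 30% | 5% vs 3% | 4.7% | 2.9% |
| 10% | 50% vs 20% | 5% vs 2% | 9.6% | 2.9% |
| 10% | 50% vs 10% | 5% vs 1% | 19.4% | 2.9% |
| 20% | 50% vs 30% | 10% vs 6% | 12% | 3.3% |
| 20% | 50% vs 20% | 10% vs 4% | 29% | 3.3% |
| 20% | 50% vs 10% | 10% vs 2% | 58.7% | 3.3% |

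Reversing the attribution reverses the direction: at 10% risk with 20% vs 50% attributed, the test falsely favours the drug 9.6% of the time.

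*True excess, 20% in Arm 1 against 10% in Arm 2: chance of detecting it*

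| Comparison | Risks compared | Detected |
|---|---|---|
| All-cause | 20% vs 10% | 44% |
| Related, 50% attributed in both arms | 10% vs 5% | 19% |
| Related, 20% attributed in both arms | 4% vs 2% | 4% |
| Related, 25% vs 50% attributed | 5% vs 5% | 1% |

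The loss of power needs no bias. Equal attribution is enough.

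**The case against.** The strongest reply is that serious harm is not left to attribution. Deaths, intensive care transfer and both forms of ventilation are compared regardless of cause, and in patients hospitalized with COVID-19 they plausibly make up many of the serious events. That stands, and it rules out a reading a reader might otherwise reach: that the trial's whole comparison of serious harm rests on unblinded judgement. The documents do not support that. The gap is narrower but remains, because these outcomes are efficacy criteria in the ITT and PP sets and miss serious events that lead to none of them.

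A reader might also take it as stated that investigators who know the arm decide relatedness, or that the new tablet will be blamed more often. The plan does not say who judges association. Knowledge of the arm is a reasonable inference from the open design, and the direction of any difference is unknown.

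The 59% figure should not be read as the expected error. It needs a 20% SAE rate and five-fold differential attribution. A milder setting (10%, with 50% against 30%) gives about 5%.

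Finally, SAEs are collected without a filter, descriptive statistics are promised for all safety indicators collected, and sections outside the synopsis may hold fuller tables. This tempers any statement about the plan as a whole. But the descriptive provision sets out no all-cause SAE comparison between arms, and the restricted wording is identical in both lists supplied.

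**Conclusion.** The point holds as a gap in the safety indicators. The one listed SAE comparison counts only events judged related to treatment, in an open trial with no blinded causality review described, and no all-cause SAE comparison is listed. The all-cause comparisons of death, intensive care and ventilation narrow the gap without closing it.

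Under the assumed rates, differential attribution alone gives a false difference in about 5% to 59% of trials, against about 3% for an all-cause test. Attributing half of the events in both arms cuts power for a true doubling from 44% to 19%. These figures rest on assumed SAE and attribution rates, on the full 100 per arm, and on relatedness being judged with the arm known. The structural point, that randomisation does not protect a comparison filtered by causality, does not depend on the particular rates. The primary efficacy analysis is unaffected. The change should be made, but it is a modest one.

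**What to change.** In both safety lists, make the between-arm SAE indicator the percentage of patients with any SAE regardless of causality, reported with the risk difference and its 95% confidence interval. Keep related SAEs as a supportive indicator.

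Reword the safety population at the same time. Under Population analysis it requires a dose of the study drug, which read literally leaves out the standard-therapy arm, and a between-arm SAE rate needs both arms.

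The cost is one line in two lists, one change to the population wording and one extra table. SAEs are already followed, including by telephone after discharge, so no new visits, data collection or patients are needed. If an all-cause SAE table already exists in a section outside the synopsis, these lists need only be aligned with it.
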